8.2 Statistical Methods

Descriptive Statistics

Sample Size Computation and Power Analysis:

The sample size for this pilot study is set at 12 subjects for logistical and financial reasons. This is similar in size to other exploratory studies and will provide adequate data for estimation purposes for planning future studies. With 12 subjects, the study is intended to be for estimation purposes only.

Statistical Analysis Plan:

Data Analysis - The statistical analysis will provide descriptive summary statistics for categorical and continuous outcomes. Categorical variables will be described by their count and proportion of occurrence while continuous, normally distributed variables will be described by their mean and standard deviation; and continuous, non-normally distributed variables will be described by their median and range. The paired or unpaired Wilcoxon tests will be used to quantify differences in numerical outcomes while the Fisher's exact test and the McNemar's or Bowker's tests will be used to quantify changes in categorical variables.

If missingness occurs at random a mixed model will be utilized to assess the change in the lesion over time. A sensitivity analysis will be performed using the last observation carried forward and the results will be compared to that of the mixed-model.

Effect sizes will be estimated for the appropriate statistical tests that will be used for group comparisons in future studies. This will enable more accurate power and sample size estimates moving forward.

Bioinformatic Analysis:

RNA-seq analysis: We will use our recently developed LinNorm program (<https://www.bioconductor.org/packages/release/bioc/html/Linnorm.html>) to process RNA-seq data and detect differentially expressed genes (DEGs) by comparing the RNA-seq profiles. We will first find DEG between responsive and non-responsive samples from the same individual by using paired or unpaired Wilcoxon rank-sum test (depending on how the samples are collected). We will then rank each gene in the DEGs based on the occurrence frequencies in all 12 subjects

to find common DEGs for responsiveness (use permutation test to determine the p value). For the top ranked genes (common DEGs), we will use DAVID (3) and GSEA (4) software to find enriched inflammatory pathways and GO terms for the DEGs. By comparing the normal tissue with the pathogenic tissue (responsive + non-responsive) using the above approach, we will detect a common DEGs for LP pathogenesis. Hierarchical clustering (5) and Principal Component Analysis (PCA) (6) will be applied to samples for their hierarchical relationship and clustering properties. Ideally normal, responsive and non-responsive tissues should form three distinct groups. The PCA analysis will provide us a set of gene signatures that can distinguish these three types of tissues. The common DEGs for responsiveness and pathogenesis, as well as gene signature from PCA will be used for our pathogenesis or survival prediction. We will perform structure variants calling from RNA-seq data with SNPiR (7), and reconstruct gene co-expression networks with ARACHNE.(8) Additionally, we will perform de-convolutional analysis, to compare the immune profiles of responsive and non-responsive tissue and to correlate immune profiles. Predictive biomarkers will be correlated with lesional and global responses.

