Overall, 199 subjects were enrolled. A total of 161 (80.9%) completed the Day 84 visit. Within each active treatment group, the mean scores for the individual and total psoriasis lesion assessments, the Psoriasis Area and Severity Index (PASI), and the Physician's Global Assessment (PGA), as well as the mean treatable percent BSA decreased from baseline to each subsequent assessment, which indicated an overall lessening of disease severity. Based on a review of the extent of exposure, the incidence of all reported AEs, the clinical laboratory results, vital signs, and ECG findings, no safety signals or trends were observed. Overall, INCB018424

PHOSPHATE CREAM (0.5%, 1.0%, or 1.5%) was demonstrated to be safe and well tolerated when applied QD for 12 weeks to plaque psoriasis affecting 2% to 20% of the BSA.

Study INCB 18424-204 is a 2-part study of subjects with alopecia areata with Part A being open-label and Part B being double-blind, randomized, and placebo-controlled; subjects in both parts who meet prespecified criteria are eligible for an additional 24 weeks of open-label treatment. Preliminary unaudited data for this study are presented through 28 JUN 2016. Twelve subjects were enrolled in Part A, the open-label portion of the study. Of these 12 subjects, 5 subjects (41.7%) have completed the study through Week 24, and no subjects have discontinued study treatment. Forty-four subjects were randomized in Part B, the double-blind portion of the study. Of these 44 subjects, 3 subjects (6.8%) discontinued from the study, 1 subject because of an AE (pruritus judged not related to study drug), 1 subject because of subject decision, and 1 subject because of abnormal laboratory values at screening. In Part A, 8 subjects (66.7%) had a treatment-emergent adverse event (TEAE). One subject had Grade 3 SAEs of noncardiac chest pain, pulmonary mass, and sepsis judged as not related to study drug by the investigator that led to interruption of study drug; these events resolved, and the subject resumed study drug. All of the TEAEs reported in Part A occurred in 1 subject each. In Part B, 7 subjects (16.7%) had TEAEs. One subject had an SAE of nausea and vomiting (judged not related by the investigator); this event resolved with continuation of study drug. The most frequently reported TEAE in Part B was skin exfoliation, which was reported in 3 subjects (7.1%); these events were judged as not related by the investigator.

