To determine the efficacy of INCB018424 PHOSPHATE CREAM and the duration of response after discontinuation as measured by the change in Pruritus NRS, (week 0 to week 4, week 0 to week 8, weeks 4 to 8, weeks 8 to 12), Change in Skindex-16 (week 0 to week 4, weeks 4 to 8, weeks 8 to 12), Change in Physician Global Assessment (PGA) (week 0 to week 4, week 0 to week 8, weeks 4 to 8, weeks 8 to 12), Change in BSA (week 0 to week 4, week 0 to week 8, weeks 4 to 8, weeks 8 to 12), Change in Modified CAILS (week 0 to week 8, weeks 4 to 8, weeks 8 to 12).

Exploratory Objectives:

To predict responses and examine the pharmacodynamics of treatment through the identification of unique biomarkers and transcriptomic changes of LP at week 0 and utilizing RNA sequencing on responsive and non-responsive tissue at week 4 To correlate these biomarkers with measures of global response: Modified CAILS, PGA, BSA, and lesion count.

4 Study Design

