4.5 Secondary Study Endpoints

Change in Pruritus NRS, (week 0 to week 4, week 0 to week 8, weeks 4 to 8, weeks 8 to 12), Change in Skindex-16 (week 0 to week 4, weeks 4 to 8, weeks 8 to 12), Change in Physician Global Assessment (PGA) (week 0 to week 4, week 0 to week 8, weeks 4 to 8, weeks 8 to 12), Change in BSA (week 0 to week 4, week 0 to week 8, weeks 4 to 8, weeks 8 to 12), Change in Modified CAILS (week 0 to week 8, weeks 4 to 8, weeks 8 to 12).

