6.2 Treatment Regimen

Subjects will apply the study drug topically to LP lesions twice daily. Treatment will take place from Day 0 to Week 8.

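### The mixed model for lesion change hangs on an unverifiable condition, and its only check, LOCF, assumes that response lasts for a subject treated to Week 8 who misses Week 12

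*Combined protocol and SAP*

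**What the plan says.** Section 8.2 (Statistical Methods) gives the missing-data plan in two sentences. The first is "If missingness occurs at random a mixed model will be utilized to assess the change in the lesion over time". The second begins "A sensitivity analysis will be performed using the last observation carried forward" and goes on to set that analysis beside the mixed model. Nothing says how the condition would be judged, and no other sensitivity analysis is named. Before these sentences, and without any condition, the section lists descriptive summaries, Wilcoxon tests for numerical outcomes, and Fisher, McNemar or Bowker tests for categorical ones.

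On timing, section 6.2 states "Treatment will take place from Day 0 to Week 8". In Table-2 the only visit after Week 8 is Week 12. The secondary objective in section 3 includes "the duration of response after discontinuation", and section 4.5 lists the Week 8 to 12 change in Modified CAILS among the secondary endpoints.

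On withdrawal, sections 5.4.1 and 5.4.2 capture data when a subject withdraws, add a 4-week observation phase and rule out replacement. Section 10.3 requires an explanation for every missing item on the case report form. No analysis rule uses those explanations.

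**The concern.** There are two linked weaknesses.

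First, whether data are missing at random (MAR) depends on the values that were not seen. Recorded reasons can make the assumption more or less plausible, but the observed data cannot confirm it. As a trigger for using the model, the condition leaves the choice open until after the data are in.

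Second, a sensitivity analysis should ask what happens if the missing subjects did worse than the model predicts. LOCF asks something else: what if nothing changed after the last visit? For the off-drug interval that is the favourable answer to the durability question. If subjects seen at Week 12 have worsened on average, LOCF moves the estimate toward maintained response, away from the scenario a reader would worry about.

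The stake is the quality of the estimate. Sections 8.1 and 8.2 present the trial as a source of estimates for planning later studies. A check that cannot reveal relapse gives little support to the durability estimate.

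**Working it through.** The plan gives no figure on missing data to reproduce. Its only computed design figures (about 88 and about 108 subjects, section 8.1) do not enter this point.

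**Inputs.** N = 12 (section 4.2). Last on-drug assessment at Week 8 (sections 4.1 and 6.2); off-drug assessment at Week 12 (Table-2). The number missing Week 12, *k*, is an assumption, shown from 0 to 4.

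**Step 1: what LOCF does to the endpoint.** If Week 12 is missing, LOCF sets Y12 = Y8, so Y12 − Y8 = 0. With *k* of 12 missing Week 12,

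LOCF mean change = [(12 − k) × observed mean + k × 0] / 12 = (12 − k)/12 × observed mean.

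| k missing | LOCF mean as share of observed mean |
|---|---|
| 0 | 12/12 = 100% |
| 1 | 11/12 = 92% |
| 2 | 10/12 = 83% |
| 3 | 9/12 = 75% |
| 4 | 8/12 = 67% |

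**Step 2: what *k* might be.** Section 2.4 gives three rates for the same cream, none in lichen planus:

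- Alopecia areata Part A, open-label: 0 of 12 had discontinued treatment (interim data). Expected: 0 of 12.
- Alopecia areata Part B, also interim: 3/44 = 6.8%. Expected: 12 × 0.068 = 0.8. Chance of at least one: 1 − (41/44)^12 = 57%.
- The 12-week psoriasis study: "A total of 161 (80.9%) completed the Day 84 visit". So 199 − 161 = 38, and 38/199 = 19.1%. Expected: 12 × 0.191 = 2.3. Chance of at least one: 1 − (161/199)^12 = 92%.

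The assumed range of 0 to 4 covers all three expected counts. Discontinuing treatment or not completing a study is not the same as missing one visit, so these rates are only a guide.

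**Step 3: direction.** Take an illustration with assumed values. Ten observed subjects worsen by 2 points and two missing subjects in truth worsen by 8.

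- True mean: (10 × 2 + 2 × 8)/12 = 3.0.
- MAR analysis: about 2.0, if the missing subjects resemble the others up to Week 8.
- LOCF: (10 × 2)/12 = 1.67.

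LOCF falls on the far side of the MAR result from the truth.

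**Step 4: when MAR is true.** A simulation of 12 subjects (4,000 runs) had a true Week 8 to 12 worsening of 4.0. The chance of missing Week 12 depended on the Week 8 score, and on average 2.8 of 12 were missing. The MAR estimate averaged 3.99 and LOCF averaged 3.22. Here LOCF disagrees with the model although the model is right.

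**Step 5: the Wilcoxon test.** The standard signed-rank test drops zeros. In one example with 10 observed and 2 carried-forward subjects, p was 0.0039 with or without the carried-forward zeros. LOCF does not stress that test either.

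**The case against.** The strongest reply has five parts.

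- **Withdrawal data.** A reader might infer that a subject withdrawn for progression has the value before worsening carried forward, or that anyone missing after drug is stopped is credited with no loss of response. The documents do not support either as a general statement. Sections 5.4.1 and 5.4.2 capture data at withdrawal and add four weeks of observation, so the value carried may already be a worsened or off-drug one. The exact zero for loss of response since stopping applies to subjects treated to Week 8 who then miss Week 12.
- **Scope.** It is tempting to say that the whole durability objective is biased. The mixed-model and LOCF sentences concern lesion change, which clearly reaches only Modified CAILS. For pruritus NRS, Skindex-16, PGA and BSA no missing-data method is clearly stated, which is a separate gap.
- **LOCF is a comparator.** It is set beside the mixed model and does not by itself bias the reported estimate. That is right. The complaint is that it is a poor check.
- **A fallback exists.** A reader might infer that nothing is left if the condition fails. Descriptive summaries and Wilcoxon tests are named unconditionally. They carry no missing-data rule, however, so the gap narrows without closing.
- **Size.** A single shrinkage of about 19% would rest on the highest of the three rates in section 2.4. A range is needed.

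These points limit the concern. None makes the condition testable or turns LOCF into a test of departure from MAR.

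**Conclusion.** The point holds within these limits. The condition on the mixed model cannot be verified from the data. For a subject treated to Week 8 who misses Week 12, the only sensitivity analysis assumes durability instead of testing it. Early withdrawers with recorded off-drug visits are less affected. The Week 4 primary endpoint is on treatment and does not have this problem.

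The effect on the LOCF result runs from none with nobody missing to a one-third reduction with 4 of 12 missing. This rests on the assumed counts, because the plan gives no dropout rate. The movement is toward maintained response only if the observed subjects worsen on average.

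The point is minor: a secondary endpoint in a 12-subject study meant for estimation, with no error-rate claim at stake. It is worth making because the estimates are the trial's product and the repair is cheap.

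**What to change.** In section 8.2:

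1. Fit the mixed model to all treated subjects without the condition, and state missing at random as an assumption. Section 8.3 already defines the population as everyone with at least one dose, although its label suggests completers.
2. Replace LOCF with a departure-from-MAR check for missing values: a delta shift starting at the model's own prediction and ranging up to full loss of response. At that extreme, set the missing value to the worse of baseline and the last observed value. Baseline alone could flatter a subject already worse than baseline.
3. Report the number of missing Week 12 values, the reasons already collected on the case report form, and whether the estimate changes materially across the range.

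The cost is a few sentences of SAP text and a few extra runs. Visits, treatment and data collection do not change. The downside is that the sensitivity results may look less favourable.

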4.1 General Description

This is a single center, exploratory, open-label, single-arm design study of 12 patients. Treatment naïve and treatment refractory patients with LP will be treated with INCB018424 PHOSPHATE CREAM. Patients who are non-responders, to physician choice standard of care, will undergo a washout period and will be enrolled in the study.

Multiple safety studies have been conducted with INCB018424 PHOSPHATE CREAM (see Safety) and a dose of 1.5% cream BID on up to 20% BSA is deemed safe. (Investigator's Brochure) The Within each cohort, the maximum reduction from baseline in the total psoriasis lesion assessment scores for the treated lesions was observed at the end of treatment (Day 28). (Investigator's Brochure) Therefore, we propose a single center, exploratory, open-label, single-arm design study of 12 patients. Treatment naïve and treatment refractory patients with LP will be treated with INCB018424 PHOSPHATE CREAM.

Individuals with LP involving less than 20% of the BSA will be eligible. Individuals must have 4 lesions at baseline, however, a minimum of 10 lesions is ideal, which are at least 5mm in diameter. 10 lesions are ideal as 2 lesions will be index lesions and 8 or more lesions will be selected from as responsive or non-responsive at 4 weeks. All lesions except for one index lesion will be treated and all lesions will be annotated, photographed, and scored. The rationale for a minimum of 8 lesions is based upon the assumption of a 50% response rate at 2 weeks. With 8 lesions, there would be a less than 1% chance that all 8 lesions would respond. Ideally, the 2 index lesions will be 10mm in diameter but this is not a requirement. Prior treatment will be allowed; however, a washout period of 2 weeks for topical and 4 weeks for systemic agents is required. At the washout period, individuals will undergo evaluation with a PGA, BSA calculation, and have the 2 largest, representative lesions selected for evaluation using a modified CAILS score lesion A- treatment index lesion and B-index control lesion. The determination of which lesion receives treatment and which is a control will be determined randomly. The additional lesions will be photographed, measured, scored, and recorded with Modified CAILS scores as well. The later calculations will be used for the determination of responsive and non-responsive lesions. Additional Pruritus measures using the NRS and Skindex-16 will be collected at that time.

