Individuals will then initiate treatment on all lesions of LP BID and will be evaluated weekly and assessed by PGA, BSA, lesion count; Modified CAILS, Pruritus NRS, and Skindex-16 between weeks 0-4 (see Appendix). Week 4 will be the primary endpoint; however therapy will be continued for an additional 4 weeks. Therapy will be stopped and the individuals will be evaluated at week 8 and assessed by PGA, BSA, lesion count, Modified CAILS, Pruritus NRS, and Skindex-16. Laboratory and safety monitoring will occur at weeks 1, 2, 3, 4, and 8, and 12. 3D Photographs will be taken at weeks 0, 1, 2, 3, 4, 8, and 12. Individual lesions will be circled at that time and the exact volume of each lesion will be measured. Up close photos will be taken of the disease and normal tissues attained at weeks 0 & 4.

Tissue will be collected for RNA sequencing at week 0 and 4. Blood collection will include the isolation at week 0, 2, and week 4, 5mL vials of blood which will be separated and the serum and cell pellet will be stored for future analysis. Five skin biopsies will be taken during the study. At week 0, up to two 3mm tissue biopsies will be taken from lesional skin and one biopsy will be taken from normal appearing skin. The initial biopsy of lesional tissue and control will be

annotated. At week 4, up to two 3mm biopsies will be taken from lesional responsive tissue and lesional refractory tissue. Responsive and non-responsive lesions will be determined by the change in Modified CAILS between week 0 and 4. Responsive will require a 50% reduction in Modified CAILS and non-responsive can have progression, no change, or up to a 50% reduction in Modified CAILS. The lesions will be chosen using full body photographs taken at week 0. Up to 60 samples will be snap frozen and stored in the tissue biobank. Once completed, RNA sequencing will be performed on the 60 tissue samples and analysis will be performed. Paired analysis of treatment responsive and refractory lesions will be made as well as treated and untreated lesions.

Nucleic Acid Extractions: RNA will be extracted from a total of 50 um of fresh tissue using the Qiagen FFPE RNeasy Micro extraction Kit according to manufacturer's recommendation.

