4.2 Number of Subjects

12 subjects will be enrolled in this study.

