Week 4 Visit we will:

- Perform a physical exam, check vital signs and ask about side effects or health problems since last visit
- Exam skin lesions to note any changes
- Take photographs of skin lesions to document any changes
- Draw a blood sample
- Perform a skin biopsy (up to 2 tissue samples will be taken)
- Perform a tap stripping on skin
- Dispense study drug

7.7 Visit 7

Week 8 Visit we will:

- Perform a physical exam, check vital signs and ask about side effects or health problems since last visit
- Exam skin lesions to note any changes
- Take photographs of skin lesions to document any changes
- Draw a blood sample

7.8 Visit 8

Week 12 Visit we will:

- Perform a physical exam, check vital signs and ask about side effects or health problems since last visit
- Exam skin lesions to note any changes
- Take photographs of skin lesions to document any changes
- Draw a blood sample

8 Statistical Plan

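### The per-subject Wilcoxon step for differentially expressed genes compares at most one biopsy with one, so it returns p = 1.0 for every gene and the ranking across 12 subjects has nothing to rank

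*Combined protocol and SAP*

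**What the plan says.** Section 8.2 (Bioinformatic Analysis) sets out a sequence of steps.

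- **Calling genes.** "We will first find DEG between responsive and non-responsive samples from the same individual by using paired or unpaired Wilcoxon rank-sum test". The choice between paired and unpaired is left to how the samples turn out to be collected.
- **Ranking.** "We will then rank each gene in the DEGs based on the occurrence frequencies in all 12 subjects", with a permutation test supplying the p-value. The top-ranked genes go into DAVID and GSEA, and the common genes feed the prediction work.
- **Normal versus diseased tissue.** "By comparing the normal tissue with the pathogenic tissue (responsive + non-responsive) using the above approach", the plan derives a second common gene list, for pathogenesis.

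Section 4.1 fixes the tissue. At week 0, "up to two 3mm tissue biopsies will be taken from lesional skin and one biopsy will be taken from normal appearing skin". Later, "At week 4, up to two 3mm biopsies will be taken from lesional responsive tissue and lesional refractory tissue". The week-4 visit in Section 7.6 repeats the limit of two samples. Section 4.1 gives five biopsies per subject and up to 60 samples in all.

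Section 8.2 gives no p-value cutoff, sidedness, fold-change rule or multiplicity rule for the gene-level tests.

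**The concern.** Counting in how many subjects a gene is differentially expressed requires a decision on that gene within each subject. The only test named for that decision is a Wilcoxon test, and a rank test on one sample per group cannot distinguish any gene from any other. If every subject's list is empty (or, with a very loose cutoff, contains every gene), the counts are all tied and the permutation step has nothing to separate.

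The second comparison inherits the problem and adds another. Normal skin is biopsied only at week 0, while tissue can be classed as responsive or non-responsive only after 4 weeks of treatment. Tissue class is therefore confounded with time and drug.

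At stake is the exploratory objective of finding genes linked to response, which Section 8.1 offers as part of the case for a 12-subject study. If the wording is left as it is, the replacement test will be chosen with the data in view.

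**Working it through.** **1. Samples per subject.** Week 0: 2 lesional + 1 normal = 3. Week 4: 2 at most. Total 5 per subject, and 12 × 5 = 60, which reproduces the plan's figure. The week-4 limit of two therefore covers both classes together, so the within-subject comparison is at most 1 responsive against 1 non-responsive.

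**2. Smallest attainable p within one subject.** For the two-sided exact rank-sum test with group sizes m and n, the minimum is 2/C(m+n, m), capped at 1:

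| Grouping | Minimum p |
|---|---|
| 1 vs 1 (responsive vs non-responsive) | 2/2 = 1.0 |
| 1 vs 2 (normal vs both week-4 samples) | 2/3 = 0.67 |
| 1 vs 4 (normal vs all lesional samples) | 2/5 = 0.40 |
| 2 vs 2 | 2/6 = 0.33 |
| 2 vs 3 (best split of five biopsies) | 2/10 = 0.20 |

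The paired signed-rank test has minimum 2/2^n for n pairs; with one pair it is also 1.0. At 1 vs 1 the minimum is the only attainable value, so every untied gene gets the same p.

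**3. Other ways of computing p.** An uncorrected normal approximation gives 0.317 for every gene at 1 vs 1, and no less than 0.083 for any grouping above (2 vs 3). One-sided exact p at 1 vs 1 is 0.5 or 1.0, which shows direction only. None meets a conventional cutoff.

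**4. Loosening the cutoff.** The plan does not propose this. A cutoff of 0.33 (2 vs 2) or 0.20 (2 vs 3) would pass that share of null genes by chance. With an assumed 15,000 to 20,000 genes, that is 5,000 to about 6,700, or 3,000 to 4,000.

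**5. An across-subject signed-rank test instead.** With 12 pairs the minimum p is 2/4,096 = 0.00049. For any gene to pass Benjamini-Hochberg (BH) at 5% among G genes, at least p_min × G/0.05 must pass together: 0.000488 × 15,000/0.05 = 146.5, so 147; for G = 20,000, 195.3, so 196.

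Fewer pairs are likely, because a subject contributes only if both tissue classes are present. Section 4.1 offers a response rate, stated for 2 weeks: "The rationale for a minimum of 8 lesions is based upon the assumption of a 50% response rate at 2 weeks". Applying it at week 4, and assuming lesions respond independently:

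- Minimum 4 lesions, of which 3 are treated: 1 − 2 × 0.5³ = 0.75, × 12 = 9 subjects.
- 8 treated lesions: 1 − 2 × 0.5⁸ = 0.992, × 12 = 11.9 subjects.

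With 9 pairs the minimum p is 2/512 = 0.0039, and BH needs at least 1,172 (G = 15,000) to 1,563 (G = 20,000) genes to pass together.

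**6. Signed-rank against a moderated-variance model.** Simulated with 15,000 genes, 12 pairs and normal data, all assumed; the gene-variance distribution suits the moderated model. Mean true genes found at BH 5%, as ranges over repeat simulations:

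| True genes, standardised paired difference | Signed-rank | Moderated t |
|---|---|---|
| 100 at 1.5 | 0 | 69–71 |
| 300 at 1.5 | 11–24 | 253–255 |
| 300 at 2.0 | 233–239 | 298 |

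The zero in the first row follows from step 5: 100 true genes cannot easily supply the 147 needed.

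**The case against.** The strongest reply is that an across-subject test was intended. Section 4.1 announces a paired analysis of responsive and refractory lesions, and pairing is natural when each subject supplies one pair. On that reading the test runs, with a floor of 0.00049 at 12 pairs. The text is open to this reading, but a single across-subject test yields one gene list, so there are no per-subject lists to count. One could count subjects with the same direction of change, but the plan does not say so. Under either reading the two sentences do not fit together.

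Second, Section 8.2 says the LinNorm program will detect differentially expressed genes. It attaches no decision rule to that program; the only test named for this step is the Wilcoxon.

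Third, the study is exploratory and meant for estimation, with 12 subjects chosen on logistical and financial grounds. That limits how much this matters, but does not make the step workable.

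Some criticism of the supporting figures stands. The 9-pair case is pessimistic if most subjects have the ideal 10 lesions. The simulation favours the moderated model by construction, and its gene counts and effect sizes are assumed. The loosened cutoffs are hypothetical. None of these is needed for the main conclusion, which rests on steps 1 to 3 of the working. The week-0 versus week-4 confounding and the missing multiplicity rule are separate defects and should be judged on their own.

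**Conclusion.** The concern holds: the step is wrong as written, not merely under-described. With at most one responsive and one non-responsive biopsy per subject, the two-sided exact Wilcoxon p is 1.0 for every gene. The normal-versus-pathogenic comparison cannot go below 0.67. These results need only the plan's sample counts and the two-sided exact form of the test; other forms change the value but still reach no conventional cutoff.

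The parts affected are the frequency ranking, its permutation p-value, the DAVID and GSEA steps, and the common-gene part of the prediction work. The PCA and its signature, clustering, deconvolution, and the primary, secondary and safety endpoints do not depend on it. This should be fixed, but it does not threaten the trial's main results.

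**What to change.** Amend Section 8.2 before the sequencing data are analysed.

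- **Replace the per-subject test and frequency ranking** with one across-subject analysis per gene on the normalised data: tissue class as the effect, subject as the block, BH false discovery rate of 5%. A moderated-variance linear model is preferable to an across-subject signed-rank test, for the reasons in steps 5 and 6.
- **Responsiveness:** compare week-4 responsive with week-4 non-responsive tissue.
- **Pathogenesis:** compare week-0 normal with week-0 lesional tissue in the same blocked model. This removes the confounding with time and treatment.
- **If permutation is kept:** swap labels only within subjects who have both tissue classes, and pool over genes or use a global statistic. Swapping gene by gene has the same floor of 2/4,096 with 12 pairs.

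These two contrasts do not test whether week-0 expression predicts later response. Section 3 includes that aim, so its analysis needs its own statement.

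The cost is SAP wording and standard software, with no new samples or visits. The linear model makes a mild distributional assumption that a rank test avoids.

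### Section 8.2 ranks common DEGs by a per-subject count with no direction rule and an undefined permutation, and the per-subject test that feeds the count cannot call any gene

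*Combined protocol and SAP*

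**What the plan says.** The gene-expression analysis is in the Bioinformatic Analysis part of Section 8.2. It has three steps.

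- Calls within each subject: "We will first find DEG between responsive and non-responsive samples from the same individual by using paired or unpaired Wilcoxon rank-sum test".
- Ranking across subjects: "We will then rank each gene in the DEGs based on the occurrence frequencies in all 12 subjects".
- Inference: "to find common DEGs for responsiveness (use permutation test to determine the p value".

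No cut-off, sidedness or fold-change rule is given for the call. Nothing says whether up-calls and down-calls are pooled or counted separately, and nothing says what is permuted. A second contrast, for disease rather than response, reuses the method: "By comparing the normal tissue with the pathogenic tissue (responsive + non-responsive) using the above approach".

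Section 4.1 sets the number of samples: "Five skin biopsies will be taken during the study", and "At week 4, up to two 3mm biopsies will be taken from lesional responsive tissue and lesional refractory tissue". Section 7.6 also allows at most two tissue samples at week 4. Section 4.1 adds that responsive and refractory lesions will be compared as pairs.

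**The concern.** For a question about response, the direction of change is the signal. A gene that is higher in responsive tissue in half the patients and lower in the other half has no consistent link with response, yet an unsigned count treats it like a gene that always moves one way. A permutation test repairs this only if its statistic carries direction, and the plan does not say that it does.

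The common-DEG list feeds the pathway enrichment and the prediction work, and predictive biomarkers are then to be correlated with lesional and global response. Section 8.1 justifies a 12-subject study partly by the response biomarkers it should yield. A ranking that cannot be built, or that mixes consistent with inconsistent genes, weakens that return.

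**Working it through.** **1. Samples per subject.** Section 4.1 gives up to 2 lesional and 1 normal biopsy at week 0, and up to 2 at week 4. Section 4.2 gives 12 subjects. 12 × (2 + 1 + 2) = 60, which matches the plan's own total ("RNA sequencing will be performed on the 60 tissue samples"). The responsive versus non-responsive contrast is therefore 1 versus 1 within a subject.

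**2. Can the per-subject test call a gene?** The smallest two-sided exact rank-sum p for a versus b samples is min(1, 2/C(a+b, a)).

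| Samples | Smallest two-sided p |
|---|---|
| 1 vs 1 | 1 |
| 1 vs 2 | 2/3 = 0.67 |
| 1 vs 4 | 2/5 = 0.40 |
| 2 vs 2 | 2/6 = 0.33 |

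The signed-rank test on a single pair also gives 1. At a conventional 0.05 no gene is called in any subject, every count is 0 and there is nothing to rank. This covers normal versus lesional tissue too (1 vs 2, or 1 vs 4 if the week-0 lesional samples are added).

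**3. What the count does if genes are called another way, for example by fold change.** All 2^12 = 4,096 within-patient label swaps were enumerated. The direction-specific count is the larger of the up-count and the down-count.

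| Up / down | Unsigned count | Label-swap p, unsigned | Label-swap p, direction-specific |
|---|---|---|---|
| 12 / 0 | 12 | 1 | 2/4096 = 0.00049 |
| 6 / 6 | 12 | 1 | 1 |
| 8 / 4 | 12 | 1 | 0.39 |
| 10 / 0 | 10 | 1 | 0.0020 |
| 9 / 0 | 9 | 1 | 0.0039 |

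With 1 versus 1, a swap only changes the sign of the difference, so an unsigned call with a symmetric cut-off is the same in all 4,096 relabellings.

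**4. Other permutation schemes.** Shuffling gene identities within a subject gives P(count ≥ 10 of 12) = 5.5 × 10⁻⁹ at an assumed 10% call rate and 4.5 × 10⁻⁶ at 20%. That is far from 1, but a 5 up / 5 down gene gets the same p as a 10 up / 0 down gene. For 1 normal versus 2 lesional samples, relabelling is not a sign flip. If only one of the three labellings produces a call, a count of 12 has p = (1/3)^12 = 1.9 × 10⁻⁶.

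**5. Effect on the ranking (simulation; no input is from the documents).** Assumed: 15,000 genes, of which 150 shift consistently with within-patient SD 0.6; null genes have log-normally distributed SDs; a call is |log2 ratio| > 1; 12 pairs. Entries are the share of true genes in the top 150.

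| Mean log2 ratio | Null SD: median, log-SD | Unsigned count | Up minus down | Paired t |
|---|---|---|---|---|
| 1.0 | 0.5, 0.5 | 16% | 70% | 87% |
| 1.5 | 0.5, 0.5 | 70% | 97% | 99% |
| 1.0 | 0.5, 0.3 | 51% | | |
| 1.0 | 0.4, 0.3 | 74% | | |
| 1.0 | 0.3, 0.3 | 91% | | 87% |
| 1.5 | 0.4, 0.3 | 98% | | |

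Repeat runs differ by a point or two. In every row the up-minus-down count and a moderated paired statistic matched or beat the unsigned count. The plain paired t did not (fifth row).

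**6. Informative pairs.** Section 4.1 assumes a 50% lesion response rate (stated for 2 weeks). With k selectable lesions and independence, a subject has both lesion types with probability 1 − 2 × 0.5^k. This is 0.99 for k = 8 and 0.50 for k = 2 (the 4-lesion minimum in Section 5.1 less 2 index lesions). If every subject had k = 2, about 12 × 0.50 = 6 pairs would be expected.

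**The case against.** The plan never says that direction is ignored. Analysts may well intend to count up-calls and down-calls separately, in which case the text only needs to say so. That stands: direction-blindness is the literal reading of an occurrence count plus silence, not a stated rule.

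A reader might also infer that the planned permutation p is 1 for every gene. The documents do not support that. They name no scheme, and p = 1 needs a within-patient swap, one sample per class and a symmetric call, all together. It does not hold for gene shuffling, nor does it carry over to normal versus lesional tissue, where the sample numbers are unequal. Only the absence of a direction rule carries over.

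Nor do discordant genes outrank fully consistent ones. A 6 up / 6 down gene ties with a 12 up / 0 down gene and overtakes only genes called in fewer subjects. The claim that the results would rest on the noisiest genes is not established either, since with quiet null genes the unsigned count does well.

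Finally, this is an exploratory objective in a pilot that Section 8.2 describes as for estimation only. Clustering, principal components and deconvolution do not use the count. That limits the weight of the point. It does not remove it, because the per-subject test still cannot supply the calls that the ranking needs.

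**Conclusion.** The point holds in a limited form. As written, the ranking cannot be produced: one biopsy per class gives a two-sided Wilcoxon p of 1 in every subject. Replacing the call alone, for example with a fold-change rule, leaves a count with no stated direction and a permutation with no stated unit. Under the literal reading, discordant genes can share the top rank, and the most natural paired permutation would give p = 1 for every gene in the responsive versus non-responsive contrast.

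The practical loss is uncertain. The share of true genes in the top 150 runs from about 16% to over 90%, depending on assumed effect size and noise that the documents do not give, so the low figure should not be quoted alone. The direction of the comparison is stable: signed counting or a moderated paired statistic was at least as good in every setting tried. The primary and secondary endpoints are untouched.

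**What to change.** In Section 8.2, replace the per-subject call and the occurrence count with one across-patient analysis.

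- For each gene take the within-patient difference, responsive minus non-responsive, and summarise it across patients with a moderated paired statistic.
- Obtain p by flipping signs within patients, and control the false discovery rate.
- Report the number of informative pairs, since some subjects may not have both lesion types.
- For the disease contrast, use the signed difference between the normal sample and the mean of that patient's lesional samples. State the permutation for it separately, because relabelling unequal numbers is not a sign flip.
- If a count is kept as a descriptive summary, give up and down separately.

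The cost is SAP wording; samples and data are unchanged. One limit should be stated. With 12 pairs the two-sided gene-wise sign-flip p cannot fall below 2/4096 = 0.0005, and with 6 pairs not below 2/64 = 0.03. If 10,000 to 20,000 genes are tested (an assumption), Bonferroni at 0.05 needs 0.000005 or less and cannot be met. Benjamini-Hochberg at 5% needs about 98 to 196 genes at the 12-pair floor (number of genes × 0.000488 / 0.05).
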